The 'fake' (placebo) laser device will appear to the subject to be an active device but will not produce any therapeutic light output. The placebo laser device is designed to have the same physical appearance as the actual (active test) laser device, including the appearance of any **visible** light output. Therefore, both the test and control devices emit light when activated that is indistinguishable to the subject. As the laser light does not put out any notable degree of heat or noise, these are not distinguishing factors for subjects between the active and control devices.

Apart from the distinction of whether the subject receives the study procedures with the actual or the fake laser device, all subjects and investigative parties will adhere to all phases of the entire protocol design.

DOUBLE BLIND DESIGN

This clinical study will be a double-blind design, such that neither the subject nor the investigator will be aware of whether a subject is receiving the study procedures with the active (test procedure group assignment) or the 'fake' (placebo procedure group assignment) Erchonia® FX-635™ until after the study is completed.

Maintenance of study double-blind throughout the entire course of the study will be achieved through the following means:

- 1) Each subject will be randomly assigned to Procedure Group A or to Procedure Group B by the independent study Monitor. Subjects assigned to Procedure Group A will be treated with the Erchonia® FX-635™ A and subjects assigned to Procedure Group B will be treated with Erchonia® FX-635™ B. Only the study Sponsor will know which label ('A' or 'B') corresponds to the actual (test) FX-635™ device and which label corresponds to the 'fake' device until the final study data analysis is complete. The Sponsor will ensure that this information is stored and maintained confidentially at the Sponsor's work site. This knowledge will not be shared with the investigators, the subjects, or the study Monitor until the final data analysis is complete.

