corresponds to the fake device. The Engineer will not reveal this information to any source (investigators, subjects, CRO, or Sponsor) until the final study data analysis is complete and the Post-Study Open-Label phase begins.

Once a subject has signed the informed consent form, the Principal Investigator will contact the Sponsor (via email or phone) who will act as the central source for providing sequential subject procedure group assignment.

SUBJECTS

Subject Sample

Subjects will be males and females aged 18 years or older who have diagnosed diabetic peripheral neuropathy with pain persisting over at least the past three months.

Sample size

There will be 64 qualified subjects enrolled in this clinical study:

32 subjects in the active procedure group
32 subjects in the control procedure group

Rationale for sample size

Based on the following parameters established for the purposes of assessing efficacy of the Erchonia® FX-635™ in this clinical study ...:

- Individual subject success criteria defined as a 30% or greater reduction in self-reported Degree of Pain rating on the 0-100 VAS from baseline to study endpoint evaluation.

N.B.: The clinical relevance of a 30% change in VAS score is explained and supported in the STATISTICAL ANALYSIS PLAN section further along in this protocol document.

- Overall study success criteria of at least a 35% difference between the test device group and the placebo group, comparing the proportion of individual successes in each group.
- It is anticipated that about 55% of subjects in the test device group and about 20% of subjects in the placebo group will meet the individual success criteria, and
- intended application of a two-tailed test with an alpha value of 0.05 and Power of 0.8

...the sample size of 29 subjects per group (test group and the control group, separately) has been determined using the following reference calculator:

Hypothesis Testing: Categorical Data - Estimation of Sample Size and Power for Comparing Two Binomial Proportions in Bernard Rosner's *Fundamentals of Biostatistics*.

For the purposes of sample size calculation, it is anticipated that about one-twentieth of subjects overall may withdraw from the study prior to completion for various reasons. Therefore, the following formula is used to determine the final needed starting sample size for each group:

Final sample size = sample size X $1/(1-d)$; where d = # expected dropouts/# subjects enrolled.

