The pre-procedure washout phase comprises the 48-hour (2 day) period immediately preceding the pre-procedure evaluation phase, beginning upon waking on the first 24-hour period.

On each of the two consecutive days of the washout phase, the subject is required to record the specified measures on the washout phase subject record sheets provided by the test site in his or her home and to bring the completed forms to the test site on their pre-procedure evaluation visit.

The investigator will record the dates of the 48-hour washout phase on the subject's take-home record sheets based upon the timeframe required to satisfy the pre-procedure medication abstinence criteria, as applicable.

At the start of the pre-procedure washout phase, the subject commences his or her required abstinence from use of non-study related medications and therapies for the relief of foot pain and simultaneously commences the as-needed consumption of the study rescue medication – OTC Tylenol – for his or her foot pain, that will continue through to the end of the post-procedure evaluation phase.

PRE-PROCEDURE WASHOUT PHASE MEASURES

On each day of the two-day Pre-Procedure Washout Phase, the subject records the following measures on the supplied record sheets, as outlined in the STUDY TEST BATTERY section above.

- Visual Analog Scale (VAS) Foot Pain Rating
- Use of Study Rescue Medication (Tylenol)
- Use of Other Medications

DAY 1: PRE-PROCEDURE EVALUATIONS

The pre-procedure evaluation visit occurs on the day following successful completion of the two-day pre-procedure washout phase and comprises the following activities:

CONFIRMATION OF QUALIFYING VAS RATING

The investigator measures and records the 2 individual VAS foot pain ratings and calculates the average of the 2 VAS foot pain ratings recorded during the 48-hour pre-procedure washout phase. The 2-day average washout phase VAS foot pain rating must be 50 or greater for the subject to proceed with study participation. If the 2-day average washout phase VAS foot pain rating is less than 50, the subject's participation in the study ends at this time.

CONFIRMATION OF STUDY QUALIFICATION

If more than 7 days has passed since initial study qualification evaluation and the pre-procedure evaluation phase, the investigator will confirm with the subject that the information attained during study qualification evaluation has not since changed. If any

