 5. The FX-635™ Laser is activated
 6. The laser diodes laze each of these 3 areas for 15 minutes simultaneously.
 7. The procedures listed in 4. through 6. above is repeated for the left foot.
 8. The investigator and the subject remove the safety glasses.
 9. The subject rises and leaves the procedure administration room.

At each of the procedure administration test site visits, the investigator performs an adverse events evaluation.

PROCEDURE ADMINISTRATION PHASE MEASURES

DAILY MEASURES

Commencing on the same day as the first study procedure administration with the Erchonia® FX-635™ is administered, the subject will begin to record the required information in the Subject Daily Diary, as applicable, at home.

FOLLOWING EACH PROCEDURE ADMINISTRATION

Within 10 minutes following administration of each of the first 11 study procedure administrations with the Erchonia® FX-635™, the subject will record the following at the test site:

- Visual Analog Scale (VAS) Degree of Foot Pain Rating
- Adverse Events Evaluation

POST-PROCEDURE ACTIVITIES

POST-PROCEDURE EVALUATION PHASE

The post-procedure administration evaluation phase of this study will commence immediately following completion of the procedure administration phase and will last 3 months (about 12 weeks).

POST-PROCEDURE EVALUATION VISITS AND MEASURES

There will be 4 post-procedure evaluation visits. The first post-procedure evaluation visit will occur at the test site, and the remaining three post-procedure evaluation visits will take place at the subject's home. The subject will be provided with pre-dated case report forms on which to record the required information on each of those three post-procedure days, and a staff member at the investigator's test site will contact the individual on the designated day to remind him or her to record the required information. These visits, and the associated measures to be recorded at each visit, as listed and described, and according to the methodology outlined, in the STUDY TEST BATTERY section above are as follows:

DAILY MEASURES: AT HOME

The subject will continue to record the required information in the Subject Daily Diary, as applicable, at home, through to the 4 weeks post-procedure evaluation visit.

STUDY ENDPOINT EVALUATION: FOLLOWING COMPLETION OF THE PROCEDURE ADMINISTRATION PHASE: AT THE TEST SITE

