The study endpoint evaluation visit will occur at the test site within ten minutes following completion of the procedure administration phase, after administration of the 12th and final procedure administration with the Erchonia® FX-635™.

The following measures will be recorded at this visit:

- Visual Analog Scale (VAS) Degree of Foot Pain Rating
- Neuropathic Pain Symptom Inventory (NPSI)
- Subject Satisfaction With Foot Pain Level
- Subject Perceived Group Allocation and Rationale
- Assessment Investigator Perceived Group Allocation and Rationale
- Adverse Events Evaluation

TWO WEEKS POST-PROCEDURE EVALUATION: AT HOME

Two weeks following completion of the procedure administration phase, the following measures will be recorded:

- Visual Analog Scale (VAS) Degree of Pain Rating
- Adverse Events Evaluation

FOUR WEEKS POST-PROCEDURE EVALUATION: AT HOME

Four weeks following completion of the procedure administration phase, the following measures will be recorded:

- Visual Analog Scale (VAS) Degree of Pain Rating
- Neuropathic Pain Symptom Inventory (NPSI)
- Subject Satisfaction With Foot Pain Level
- Adverse Events Evaluation

THREE MONTHS POST-PROCEDURE EVALUATION: AT HOME

Three months following completion of the procedure administration phase, the following measures will be recorded:

- Visual Analog Scale (VAS) Degree of Pain Rating
- Neuropathic Pain Symptom Inventory (NPSI)
- Subject Satisfaction With Foot Pain Level
- Adverse Events Evaluation

OPEN-LABEL PLACEBO SUBJECT PROCEDURE ADMINISTRATION PERIOD

Following completion of the 3-month post-procedure administration phase, individual subject blinding will be broken. Subjects who had been randomized to the placebo (sham) procedure group will then be offered participation in an additional 6-week post-study open-label procedure administration period during which time they will knowingly receive the active 6-week 12-procedure administration protocol with the Erchonia® FX-635™ Laser as did the subjects initially assigned to the active test procedure group at the time of study enrollment.

Participation in the 6-week post-study open-label procedure administration period is voluntary for subjects who had been assigned to the placebo (sham) procedure group. Participation in the 6-week post-study open-label procedure administration period will not be offered to subjects who had initially been randomized to the active test laser procedure group.

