For this group, the following secondary efficacy outcome measure will be evaluated:

- d) Change in VAS rating across and between all study evaluation time points to study endpoint evaluation within and between treatment groups

- e) Changes in scores on the Neuropathic Pain Symptom Inventory (NPSI) across and between all evaluation points to study endpoint evaluation within and between treatment groups
- f) Differences in the use of rescue pain medication between procedure groups across study duration to study endpoint evaluation.

STATISTICAL METHODS

Efficacy analysis will be according to the intent to treat (ITT) principle by last observation carried forward (LOCF).

Intent to Treat: Subjects will be included in the analysis if they were randomized to study procedure group, had a valid baseline visit including the required Low Back Pain VAS recordings; and received the first study procedure administration.

Last observation carried forward: Missing data will be handled by carrying forward the last observation.

Per-protocol analysis will also be performed for the set of all subjects who were randomized to procedure group and completed the study according to the full protocol.

STATISTICAL ANALYSIS

The primary analysis of efficacy will be through the application of:

- 1) **Fisher's exact test** to compare the proportion of success between the test and the control groups, considering that randomization has been diligently conducted and important covariates between the two groups are well balanced.
- 2) **Parametric ANCOVA model** analysis with the mean change from baseline to study endpoint in foot pain ratings on the VAS as the dependent variable, procedure group as the independent variable of interest and baseline average foot pain VAS rating as a covariate. A two-tailed significance level of 5% will be considered to be statistically significant.

Covariates: The following potential covariate baseline variables will be adjusted, as applicable, through application of an ANCOVA analysis for the continuous variables and linear regression analysis for categorical variables.

- ✓ Baseline VAS rating
- ✓ Baseline NPSI total score
- ✓ Duration of foot pain
- ✓ Time since Diabetes diagnosis
- ✓ Insulin dependent versus non-insulin dependent Diabetes
- ✓ Age
- ✓ Gender

Secondary Measures Analysis

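### Subjects are unblinded at the end of the 3-month phase, whether or not the home forms are in and against the protocol's own closed-code rule, and LOCF can pass a post-session rating off as lasting relief

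*Combined protocol and SAP*

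**What the plan says.** **When the blind is broken.** The section on the open-label placebo period says: "Following completion of the 3-month post-procedure administration phase, individual subject blinding will be broken". It then offers a course at the test site to placebo subjects who want it, and adds: "Participation in the 6-week post-study open-label procedure administration period will not be offered to subjects who had initially been randomized to the active" arm. Two earlier sections give a different rule. Double Blind Design says of the A/B key: "This knowledge will not be shared with the investigators, the subjects, or the study Monitor until the final data analysis is complete". Randomization says the device engineer reveals it to nobody "until the final study data analysis is complete and the Post-Study Open-Label phase begins". These two sections differ on who holds the key but agree that it stays closed until final analysis.

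**Where follow-up is recorded.** After the week-6 endpoint visit, "the remaining three post-procedure evaluation visits will take place at the subject's home". Both arms get pre-dated forms and a staff reminder on the day. The recruitment flyer, however, puts the two-week, four-week and three-month visits at the test site, and the newspaper advertisement counts fifteen site visits (12 + 3).

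**How forms come back.** In the washout phase subjects must "bring the completed forms to the test site on their pre-procedure evaluation visit". No return route or deadline for the follow-up forms appears in the text available. The Study Test Battery gives the Principal Investigator sole responsibility for measuring the VAS marks.

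**Missing data.** Under Statistical Methods, efficacy analysis is by intention to treat with LOCF: "Missing data will be handled by carrying forward the last observation". Change in VAS and NPSI across all evaluation points is a secondary outcome.

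**The concern.** Every VAS rating during treatment, including the endpoint rating, is made within ten minutes of a session. The three home ratings are therefore the only randomised VAS evidence that relief persists away from a session, which matters for a claim about chronic pain. Two written rules weaken that evidence.

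First, the trigger for unblinding is the end of a period, not the receipt or lock of data. A late form could be completed, or a returned mark measured, after the allocation is known. Because the devices carry only the labels A and B, opening one subject's allocation can also open the code for everyone else.

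Second, LOCF can supply a 3-month value from a rating made minutes after the last session. If the effect has faded, the analysis would still show it.

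**Working it through.** **1. The unblinding rules side by side.** The open-label section acts subject by subject. It asks participants to continue their medication abstinence into the open-label course, which implies that the course follows directly on each subject's own follow-up. The other two sections allow no disclosure until the final analysis is complete. Both cannot be followed while any subject's follow-up is outstanding. The closed-code rule is also hard to apply literally: secondary data sets 2 to 5 use open-label data, so an analysis that includes them cannot be finished before that period starts. The plan needs to say which analysis or data lock it means.

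**2. Timing of the trigger.** The post-procedure phase is given as 3 months, glossed as about 12 weeks. Twelve weeks is 12 × 7 = 84 days; three calendar months are 89 to 92 days. The difference is 5 to 8 days. A phase closed at 12 weeks could therefore end before a form dated by the calendar is due.

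**3. What one unblinding reveals.** Double Blind Design states that the administration investigator knows each subject's label but not what it means. Once one subject is known to have had placebo, both labels are decoded. Using the 12-week gloss, the first subject reaches this point about 6 + 12 = 18 weeks after the first session. A subject who started k weeks later has then completed 18 − k weeks. For any k above 0 that subject is still in follow-up, and for k above 12 still in treatment. The documents give no enrolment period.

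**4. LOCF illustration.** Inputs from the sample size section: success rates of 55% (test) and 20% (placebo), two-sided alpha 0.05, power 0.80. These reproduce the plan's figure, without continuity correction:

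n = [1.960 × √(2 × 0.375 × 0.625) + 0.842 × √(0.55 × 0.45 + 0.20 × 0.80)]² / 0.35² = 28.8, rounded up to 29 per group.

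Assumptions that are not in the documents:
- the true success rate at 3 months is 20% in both arms;
- a share m of test-arm subjects return none of the three home forms;
- those subjects have their arm's average week-6 rate.

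Apparent test rate = (1 − m) × 20% + m × 55%. Apparent placebo rate = (1 − m′) × 20% + m′ × 20% = 20% for any missing share m′. False gap = m × 35 points.

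| m (test arm) | Apparent test rate | Apparent placebo rate | False gap |
|---|---|---|---|
| 10% | 18.0 + 5.5 = 23.5% | 20% | 3.5 points |
| 20% | 16.0 + 11.0 = 27.0% | 20% | 7.0 points |
| 30% | 14.0 + 16.5 = 30.5% | 20% | 10.5 points |
| 40% | 12.0 + 22.0 = 34.0% | 20% | 14.0 points |

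Unequal loss by arm is not needed: equal loss gives the same gap, because carrying forward leaves placebo at 20%. The plan's follow-up outcome is change in VAS, not response. The same logic applies there (missing share × week-6 mean difference), but the plan states no mean difference to put in.

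**The case against.** **Completion of the phase may include the 3-month record.** That is the natural reading, since the 3-month evaluation is one of the phase's four visits. A form filled in on its date, after the reminder, is blinded. A reader might infer that the 3-month ratings are unblinded as a rule; the text does not support that. What stands is narrower: a completed form may still be at the subject's home when the blind is broken, its mark may not yet have been measured, and late entry is not excluded.

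**The closed-code rule would prevent all of this.** If it governed, yes. But the open-label section says otherwise, and the protocol does not say which prevails.

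**Arm-dependent loss.** Only placebo subjects are offered a later site visit, so a reader might infer that 3-month forms will go missing mainly in the test arm. That rests on silence. The reminder applies to both arms, placebo subjects who decline have no later visit either, and the flyer places follow-up at the site. The protocol also makes the investigator keep all subject records on file, requires copies of all case report forms to be supplied, and treats an uncollected measure as a deviation. The case report forms and the monitoring plan are not in the text available and could contain a return procedure.

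**The LOCF figures are extreme.** They assume an effect wholly gone by 3 months and no home form at all. If a 2-week or 4-week form arrives, that value is carried instead. The planned per-protocol analysis would also give a partial check, though in a selected set of completers. The figures show direction and scale, not expected bias.

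**Conclusion.** The point holds in limited form. The contradiction over when the blind is broken is plain on the text, as is the absence of any form-receipt or data-lock condition in the open-label section. The carry-forward problem follows from the stated LOCF rule: 3.5 points of false gap per 10% of test-arm subjects with no home forms, under the assumed complete fading and the planned week-6 rates. No return rate or 3-month response rate is given, so the actual size is unknown.

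The exposure is in the secondary follow-up outcomes. The week-6 primary is rated at the site before the subject's own unblinding, and neither the form-receipt gap nor the carrying of session-12 values into follow-up touches it. A reader might infer that a revealed code undermines the primary for late starters. The documents do not establish this: they give no enrolment timetable, and outcomes are recorded by a separate assessment investigator who is not told the label.

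**What to change.** - Reconcile Double Blind Design, Randomization and the open-label section into one rule: no blind is broken, in either arm, until the 2-week, 4-week and 3-month forms and the diary have been received, measured and locked. Define the analysis or lock that the rule refers to.
- Protect the code for subjects still in blinded treatment or follow-up. A per-subject receipt condition alone does not do this. Either wait until the last randomised subject's blinded data are locked, or run the open-label period with staff and device labelling kept separate from the blinded part.
- Reconcile the flyer and advertisement with the post-procedure section on where follow-up takes place.
- State one return procedure and deadline for both arms (for example prepaid post with a receipt log), and report returns by arm and time point.
- Keep any form completed after unblinding out of the blinded data set.
- Do not carry the post-session-12 rating into the 2-week, 4-week or 3-month values. Analyse these on observed data, with a sensitivity analysis that varies the missing-data assumption by arm.

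The cost is a few sentences, envelopes and a log. The main downside is a later open-label offer: by the time needed to receive and lock forms, or, if all subjects must finish first, by a period that depends on the unstated length of enrolment.

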A subject participating in the post-study open-label placebo subject procedure administration period will be required to:

- ✓ continue his or her required abstinence from use of non-study related medications and therapies for the relief of foot pain and the as-needed consumption of the study rescue medication (OTC Tylenol) for his or her foot pain, through to the end of the open-label placebo subject procedure administration period;
- ✓ record the same measures as during the initial procedure administration phase, as follows:

DAILY MEASURES

The subject will record the required information in the Subject Daily Diary, as applicable, at home.

FOLLOWING EACH PROCEDURE ADMINISTRATION

Within 10 minutes following administration of each of the post-study open-label procedure administration period 12 study procedure administrations with the Erchonia® FX-635™, the subject will record the following at the test site:

- Visual Analog Scale (VAS) Degree of Pain Rating
- Adverse Events Evaluation

FOLLOWING COMPLETION OF THE PROCEDURE ADMINISTRATION PHASE: AT THE TEST SITE

The post-study open-label procedure administration period final evaluation visit will occur at the test site within one hour following completion of the 12th and final open-label procedure administration with the Erchonia® FX-635™.

The following measures will be recorded at this visit:

- Visual Analog Scale (VAS) Degree of Pain Rating
- Neuropathic Pain Symptom Inventory (NPSI)
- Subject Satisfaction With Foot Pain Level
- Adverse Events Evaluation

Following completion of the final post-study open-label test site evaluation visit, a subject's participation in the post-study open-label placebo subject procedure administration period will be complete. Subjects participating in the post-study open-label procedure administration phase will not be required to enter a post-procedure evaluation phase.

TABLE OF SUBJECT EVENTS

The following table provides a progressive summary of subject events throughout this study.

| PRE-PROCEDURE ACTIVITIES |
|--|
| 
➤ A potentially well-suited and interested candidate for participation in the study attends the investigator's office.➤ The investigator reviews the informed consent form with the candidate.➤ A candidate who voluntarily signs the informed consent form will be randomly assigned to procedure group and enter the study qualification evaluation phase of the study. |
| PRE-PROCEDURE WASHOUT PHASE: 48 HOURS |

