An adverse event (AE) is defined as any unfavorable and unanticipated sign (including an abnormal laboratory finding), symptom, or disease temporally associated with the use of a study procedure(s), whether or not it is related to the study procedure(s). The intensity of all AEs is classified as follows:

- *Mild*: A mild AE is defined as an event characterized by "awareness of symptoms which are easily tolerated."
- *Moderate*: A moderate AE is defined as an event in which "sufficient discomfort is present to cause interference with usual activity."
- *Severe*: A severe AE is defined as an event characterized by "extreme distress causing significant impairment of function or incapacitation."
- A *Serious Adverse Event (SAE)* is any AE occurring at any dose that results in:
 - Death.
 - A life-threatening event.
 - Inpatient hospitalization or prolongation of existing hospitalization.
 - Persistent or significant disability/incapacity.
 - Congenital anomaly/birth defect.

In addition, an important medical event that may not result in death, be life-threatening, or require hospitalization may be considered a SAE when, based on appropriate medical judgment, it may jeopardize the individual and/or may require medical or surgical intervention to prevent one of the outcomes listed above.

An *Unexpected AE* is any AE of which the specificity or severity is not consistent with that expected or anticipated as possible from administration of the study procedure.

A *Reasonably Related AE* is one that is possibly probably or definitely related to the study procedure (as determined by the study investigator).

REASONABLY ANTICIPATED AND POTENTIAL ADVERSE EVENTS

SAEs are not anticipated to occur in this clinical study.

Reasonably anticipated and potential AEs that may occur in this clinical study include the following:

- *Anticipated Adverse Event*: None observed or reported to date in prior clinical trials.
- *Potential Adverse Events*: include skin irritation, itching, discoloring, rash, indentations, pain/discomfort and infection.

EVALUATION OF ADVERSE EVENTS

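### Placebo subjects who take the open-label active course have no scheduled adverse event contact after the final visit; test subjects have three after the same course

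*Combined protocol and SAP*

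**What the plan says.** The section on the open-label placebo subject period offers former placebo subjects a voluntary course in which "they will knowingly receive the active 6-week 12-procedure administration protocol with the Erchonia® FX-635™ Laser". During it they are evaluated for adverse events within 10 minutes of each session and keep the daily diary at home. The final visit falls "within one hour following completion of the 12th and final open-label procedure administration" and includes an adverse event evaluation. After that, "a subject's participation in the post-study open-label placebo subject procedure administration period will be complete", and "Subjects participating in the post-study open-label procedure administration phase will not be required to enter a post-procedure evaluation phase". The Table of Subject Events lists nothing later for this period.

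For the blinded course, the Post-Procedure Evaluation Phase "will commence immediately following completion of the procedure administration phase and will last 3 months (about 12 weeks"). Adverse events are evaluated at the study endpoint visit and again, at home, at 2 weeks, 4 weeks and 3 months. The diary, which has an adverse event entry, continues "through to the 4 weeks post-procedure evaluation visit".

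The adverse events section says that potential events "include skin irritation, itching, discoloring, rash, indentations, pain/discomfort and infection".

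**The concern.** The same 12-session active course is followed by two different safety schedules. After the blinded course the plan looks for late events three times, by pre-dated home forms and a reminder from site staff. After the open-label course it does not look again.

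Some of the potential events that the plan names, such as infection, rash and discoloring, need not be visible within an hour of the last session. The protocol's own account of complications adds weight: it warns that patients with lost sensation may not notice foot injuries, which can then become seriously infected. A patient who does not notice an injury is unlikely to report it unprompted.

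At stake is late safety information from a sizeable share of the people exposed to the active device. There is also a risk that open-label and blinded adverse events are later compared over unequal periods, which would favor the shorter one.

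**Working it through.** **Step 1. The two schedules side by side** (Procedure Administration Phase, Post-Procedure Activities, open-label section).

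| Adverse event collection | Test subject, blinded course | Crossover subject, open-label course |
|---|---|---|
| During the 6 weeks | after each session; diary | after each session; diary |
| End of course | within 10 minutes of session 12 | within one hour of session 12 |
| 2 weeks, 4 weeks, 3 months after | scheduled, at home | none |
| Diary after last session | to week 4 | none stated |

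Scheduled evaluations after the end-of-course visit: 3 versus 0.

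**Step 2. Do the general rules fill the gap?** Evaluation of Adverse Events covers site visits and any other necessary time within the duration of the trial. A crossover subject's participation is complete at the final visit, so this adds no scheduled contact. Recording of Adverse Events has the investigator record events after randomization, and that sentence gives no cut-off. Subjects are also told how to report events. Spontaneous reports may therefore be recorded, but nobody is scheduled to ask.

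**Step 3. Length of scheduled observation from the first active session.**
- Blinded: 6 + 12 = about 18 weeks.
- Open-label: 6 weeks plus at most one hour, so about 6 weeks.
- With adverse event contacts to week 4: 6 + 4 = about 10 weeks. This equals the 10 consecutive weeks that the Study Test Battery gives for the blinded-phase diary.

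**Step 4. Share of active-exposed subjects affected.** Each group has 32 subjects (Sample size). If c placebo subjects cross over, the share without a post-course window is c / (32 + c). Uptake is not given, so c is an assumption.
- c = 32: 32 / 64 = 50%. This is the ceiling; every placebo subject must cross over.
- c = 16: 16 / 48 = 33%.

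Person-weeks after the active course with no scheduled contact, against the 12 weeks used for the test group: 32 × 12 = 384 or 16 × 12 = 192. The test group's planned total is 32 × 12 = 384.

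**Step 5. What a post-course window would add.** If no late event is seen in n followed subjects, the one-sided exact 95% upper bound on its rate is 1 − 0.05^(1/n).
- n = 32 (test group only): 8.94%.
- n = 48 (16 crossovers added): 6.05%.
- n = 64 (32 crossovers added): 4.57%.

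These bounds assume complete follow-up, a common 4-week window and the same late-event rate after either course.

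**The case against.** The strongest reply is that the sponsor chose this openly. The period is labelled post-study, is voluntary, and no other section promises follow-up after it. The 32 randomized test subjects already give 12 weeks of post-course data against a concurrent control, which is easier to interpret than unblinded, uncontrolled weeks in crossovers. The protocol describes the device as non-significant risk, reports no adverse events in earlier trials, and describes no late-onset effect of the laser. All of this stands, and it limits how much weight the point can bear.

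Three stronger readings are tempting, and the documents do not support them.

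- *That crossover subjects are watched for less than an hour.* They are observed for about 6 weeks. Sessions are 3 or 4 days apart, within ±1 day, so an event arising after any of sessions 1 to 11 meets a later visit or the diary.
- *That late events would go unrecorded.* Step 2 shows only that no contact is scheduled. Whether a spontaneous report would be recorded is at most unclear.
- *That pooled active-laser adverse event rates are planned on mixed follow-up.* Safety Analyses compares the randomized groups. The secondary data sets that include open-label data list VAS, NPSI and rescue medication use, up to the endpoint evaluation. The nearest text is a line after the fourth data set saying that adverse events, among other items, will be explored. It names no pooled rate or denominator.

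What survives is narrow: after session 12 there is no later session to catch a new event, and the plan schedules nothing in its place.

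**Conclusion.** The point holds as a limited gap in safety follow-up. It is a design choice that could be improved cheaply, not an inconsistency. It concerns only events that first appear after session 12 in crossover subjects: at most 32 of 64 active-exposed subjects, and 16 of 48 if uptake is 50%, a figure the documents do not give.

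The primary analysis is unaffected, because it excludes open-label data. The randomized safety comparison is unaffected over the blinded period, because both arms share one schedule to 3 months.

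The contrast of about 18 with about 6 weeks matters only if open-label and blinded adverse events are compared. The exploratory line leaves that possible, and it is unclear whether the line refers to the fourth data set or to all of them. How open-label events are attributed in the safety analysis is also unstated; that is a separate question, which the change below does not settle.

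**What to change.** Amend the open-label section to add an adverse-event-only home record, with the site reminder contact already used in the blinded phase, at 2 and 4 weeks after the 12th open-label session. Continue the diary's adverse event entry to week 4. No VAS, NPSI or satisfaction item is needed. Define this as a separate safety contact, so that the other open-label requirements still end at the final visit as now written.

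Add to the secondary analysis section that any adverse event comparison of open-label with blinded data uses a common observation window: about 6 weeks from the first active session as the plan stands, or about 10 weeks with the added contacts.

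The change reaches 4 of the 12 weeks that test subjects have, so it narrows the difference without removing it. It costs about 4 more weeks of light reporting and two staff contacts per crossover subject, an adapted form (the blinded-phase evaluations at 2 and 4 weeks also carry efficacy items), and a protocol and consent amendment with IRB review. It adds no site visit or procedure.
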